**Principal Investigator: [name], RN, FAAN**

**Title: Associate Professor**

**Department: School of Nursing**

**Protocol Version Number and Date: December 6, 2021; Version 7 External (non-Emory)**

**Collaborators:**

[name]

[name]

**B. Significance.** African Americans continue to experience the highest overall cancer mortality rates, more advanced staged cancers , and higher levels of psychological distress from cancer than non-Hispanic Whites . Additionally, cancer patients and family caregivers (FCGs) also experience high levels of psychological distress which has been linked to unmet needs for support and information from health care providers . African American patients and FCGs attribute the root cause of their psychological distress to overwhelming anxieties and concerns that cancer will lead to suffering, death, and isolation for their family member diagnosed with cancer . When interviewed, patients and FCGs recall images and horror stories of African American cancer patients who “suffered and died,” after a period of “wasting away” and in excruciating pain . The stories available to patients and FCGs are often replete with memories of a family member who waited too late and subsequently died from a cancer that spread to the point where treatment would not be effective . Despite high levels of psychological distress, African American patients and FCGs are not likely to seek mental health services  or to participate in support groups . African American cancer patients and FCGs report being receptive to interventions that incorporate cognitive and religious strategies , yet these interventions lack conceptual clarity and are rarely tailored for diverse populations .

### **Faith-Based African American Cancer Survivorship Storytelling**

The use of storytelling in interventions is emerging as a beneficial method for improving health outcomes among minority  and low literate populations . In research among African American populations, storytelling interventions have resulted in increased health promoting behaviors such as adherence to follow-up care and quality of life among breast cancer patients , increasing self-care among diabetic patients , and improvements to blood pressure . Interventions that incorporate dimensions of spirituality in group discussions may not have lasting effects  while health educational interventions delivered in faith-based institutions exclude those not religiously affiliated . However, the more troubling issue is the lack of conceptual clarity among spiritually-based interventions and the assumption of cultural equivalence in the design of these studies .

On the other hand, storytelling that incorporates the narrative of religious songs to overcome psychological distress in life-threatening is interwoven into the culture of African Americans . Additionally, in the U. S., African Americans are the most religiously affiliated population and likely to conceptualize their spirituality as a certainty that a Higher Power (God)

exists  and that this sacred being has the ability to protect, heal, and deliver them from the evils and sufferings of their worldly existence . The outward expression of this spirituality has primarily been expressed through African American storytelling and religious song which has and continues to be an important aspect of their religious culture . Moreover, during life-threatening situations, the narrative of these religious songs are used to encourage a positive sense of self through an identity as a child of God, to express a belief and faith in the promise of a life free of pain and suffering , and to promote social relationships among naturally occurring family networks . Despite this strong cultural heritage of storytelling through religious song narrative, healthcare providers and researchers have yet to fully embrace and incorporate this coping strategy into supportive care interventions for cancer patients.

**Theoretical Framework.** The development of the *Faith-Based African American Cancer Survivorship Stories Intervention* will be guided by concepts in Stress and Coping Theory  and Transportation Theory (TT) . Stress and Coping theory has been used to examine mental health promoting strategies among African American cancer patients . According to this theory, when an event is perceived as stressful, individuals use strategies to affect the stressor or to change the perception of the stressor . Among African Americans, spirituality has been a dominant strategy to change the perceived threat of cancer as an emotion focused strategy . Transportation Theory (TT) has been useful in examining the influences of narratives on health promoting behavior change among African Americans , to promote cancer screening behaviors  and adherence to cancer follow-up care . TT posits that a change in attitudes and behaviors is enhanced through the identification and emotional engagement of a viewer with the narrative. Therefore, the selection of stories incorporated into this intervention considers: 1) similarity to and identification with narrators in the recordings; and, 2) the emotional engagement of participants with selected recordings. Using this combined framework, the final selection of recordings for the intervention will consist of those most likely to influence positive affective (decrease psychological distress) and behavioral changes (engage in supportive social networks) among the targeted population.

**C. Goals/Aims:** The proposed study addresses a need to integrate spirituality with cancer care as requested among African Americans from the PI's previous research . In the PI's research with African Americans, a dominant mental health promoting strategy used in response to a cancer diagnosis is the use of religious stories and songs . African Americans have a strong cultural history of relying on religious stories and songs to overcome oppression and mental suffering encountered in their lived experience . If successful, the findings from this preliminary study will contribute to the evidence that spirituality is important to cancer care and to achieving optimal patient outcomes among this medically underserved population. More importantly, the infusion of spirituality in cancer care has the potential to reduce the high levels of psychological distress experienced among African Americans and their FCG's ; to enable them to become more engaged in their cancer care  and in supportive family relationships ; and, ultimately to improve the overall quality of life for African American cancer patients and their FCGs .

**To achieve our overall goal of improving health outcomes for African American cancer patient/FCG, the following aims will be achieved:**

**Aim 1:** Develop a series of professionally edited narrative video recordings of African American cancer patient and FCG survivorship narratives that are grounded in the strong spiritual culture of African Americans. The recordings will be professionally edited to capture the essence of patient/FCGs describing the psychological stressors encountered, and spiritually-based strategies used to in response to the psychological distress experienced, and mental health outcomes.

**Aim 2:** Evaluate the usability and acceptability of this intervention. Usability is evaluated through clarity, persuasiveness, and ease of use. Acceptability will be evaluated through enrollment, participation, and concepts of Transportation Theory (identification, engagement, and emotional response).

The work in Aim 1 and 2 is expected to provide sufficient preliminary data to support a future feasibility study that rigorously evaluates a faith-based storytelling intervention incorporating narratives from religious songs that address the psychological distress among patients and FCGs. The greater impact of this intervention is to reduce mental suffering and, assist the African American cancer patient and FCG to engage in supportive relationships during the diagnosis and treatment for cancer.

**1. Study Design:** The proposed feasibility study uses a quasi-experimental (pre-post test, repeated measures) design and qualitative methods to: 1) determine feasibility and acceptability, and 2) estimate effect sizes for outcomes of (psychological distress (primary outcome), spiritual well-being, patient-physician communication, supportive family relationships, and quality of life (secondary outcomes) of the Faith-Based African American Cancer Survivorship Storytelling Intervention among African American cancer patients and their FCGs. Qualitative methods will allow us to explore the influences of concepts from SCT and Transportation Theory on acceptability and satisfaction with the intervention. Specifically, we will use open-ended interviews to explore influences of identification, engagement, and emotional response to components of the intervention. A qualitative descriptive design  including content analysis  will be used to analyze data obtained from open-ended interviews.

**2. Study setting and sample.**

**a. Setting.** The study will be implemented in partnership with the outpatient oncology unit at the Grady Cancer Center for Excellence (GCCE). The GCCE is located within the Grady Healthcare System which is a public hospital with nearly 600,000 patient visits each year. The majority of revenues generated through Medicare and Medicaid reimbursement. The Georgia Cancer Center for Excellence (GCCE) at Grady was established by the Georgia Cancer Coalition as part of an initiative to build a statewide network of people and organizations to provide exceptional cancer treatment for all Georgians. *In 2015, GCCE provided care to 1308 cancer patients (674 men/630 women).*

**b. Population to be studied:** For this feasibility study, we will recruit a total of 40 dyads with

a recent cancer diagnosis. Patient inclusion criteria captures patients (age 30-89 years) with 1) newly diagnosed with any stage cancer; 2) treatment plans to include weekly outpatient chemotherapy; 3) previously screened and with greater than 0 level of psychological distress; and, 4) willingness to participate in all study activities including data collection; 6) willing to identify a FCG (immediate or extended family member) to participate. Participants will be excluded if they have completed surgery with no plans for chemotherapy; if they find conversations around religion or spirituality emotionally upsetting; if completed more than half of prescribed chemotherapy treatments; or, in hospice care. We will also exclude participants not able to provide informed consent.

**FCG (immediate or extended family member) Inclusion Criteria are:** 1) 18 years or older; 2) able to provide informed consent; and, 3) willingness to participate in study activities including data collection. FCG's will be excluded if they find conversations around religion or spirituality emotionally upsetting.

- c. **Sample size justification:** Since this is a feasibility study, our aim will be to compute effect sizes that will guide power calculation for testing intervention effectiveness in a future RCT. Preliminary power calculation indicated that group sizes of 40 dyads (total sample 80) will achieve 80% power to detect a minimum difference of 0.6 in a repeated measurements design having a Compound symmetry covariance structure (standard deviation of 1, within subject correlation of 0.2, and an alpha level of 0.05 assumed).
- d. **Recruitment efforts:** The success of our recruiting efforts will be dependent on developing and maintaining collaborative relationships with personnel at clinic sites. The PI has already obtained the support of GCCE Medical Director, Deputy Director, Social Worker, and Administrator. In addition, during the start-up phase of the study, we will make informal presentations about the study to center clinicians and also presentations at formal protocol start-up meetings with clinic personnel. These steps are important to introduce the study, make clinicians and staff more knowledgeable about the objectives, eligibility criteria, and logistics of the study and gain their support. We have devised a process for working with physicians and nurses and other practitioners in the clinic setting that facilitates accrual of patients into clinic studies. A major concern of clinic personnel is disruption in the flow of the clinic. The PI will meet regularly with clinic personnel to cooperate with and adhere to policies for accessing patients and to ensure that our recruiting efforts do not become burdensome for clinical staff. Clinic staff will be asked to assist with identifying patients diagnosed with a recent diagnosis of cancer. We will also review charts to confirm type cancer, stage of cancer, type and duration of planned treatment, and psychological distress screening scores.
- e. **Field Methods:** Research participants will be required to participate in intervention activities and 5 data collection interviews (1 optional open-ended interview). Interviews to complete both open-ended interviews and quantitative measures will take approximately 45 minutes. The actual administration of the intervention (viewing of video recordings) will take approximately 30 minutes with all sessions to occur over a 3-week period.

Participants will be asked to complete interviews at baseline (time of enrollment into study), after each intervention session, and at 6 weeks. These time intervals will allow us

to identify the factors and strategies that affect health outcomes over time and serve to provide preliminary data to support a larger test of the intervention. These points will also allow for comparisons with other long-term investigations of psychological distress among cancer patients. At baseline data collection we will collect demographic characteristics of participants including age, gender, education, marital status, occupation, employment status, religious affiliation, proximity to family, type and stage of cancer, type treatment, date of diagnosis, date of treatment, and psychological distress screening scores. All data collection will be conducted by phone or video conferencing platform. There will be an 6th optional open-ended interview after the interview sessions to further explore sources of and expressions of distress among participants.

*Demographic and clinical characteristics.* For patients, we will collect data on psychological distress levels (the NCCN Distress score from patient records and the Hospital Anxiety, Depression Scale (HADS)), type and staging of cancer, and type of cancer treatment by either chart review or self-report. For patients and FCGs we will collect information on age, gender, education level, health status, religious affiliation, religiosity, insured status, income, and geographic residence. The religiosity scale measures frequency of using spiritual practices such as the use of religious songs, reading religious materials, and, attending church. Collection of data for demographic and clinical characteristics will occur immediately after obtaining informed consent and before viewing the video narratives.

*NCCN Distress Scale (National Comprehensive Cancer Network)* is a well-known screening tool for distress. In the GCC, this tool is administered to all newly diagnosed cancer patients. This screening tool is a thermometer on which patients rate their distress on a level of 0-10 with 10=extreme distress and 0=no distress. The NCCN-DT will be obtained from patient records to determine eligibility for this study. We will only recruit patients with a NCCN-DT score of  $\geq 4$  which is likely indicative of high levels of distress.

*Psychological distress* levels for cancer patients will be measured with the Hospital Anxiety, Depression Scale (HADS). The HADS is a 14-item self-report scale for anxiety and depressive states for patients. Internal consistency with African American oncology patients has ranged from .77 (Anxiety) and .78 (Depression). The HADS is sensitive to change after integrative therapy interventions with scores for Anxiety (8.20 $\pm$ 4.34 to 5.79 $\pm$ 3.64); Depression (5.97 $\pm$ 4.00 to 3.96 $\pm$ 3.23). Scoring for the Anxiety and Depression Subscales of the HADS is (0-21); Normal (0-7); Borderline Abnormal Case (8-10); and Abnormal Case (11-21). Patients and family caregivers will be asked to complete this evaluation at baseline and after all of the intervention sessions.

*Quantitative Assessment of narrative quality (narrative characteristics, identification, transportation)*. Assessment of narrative quality (narrative characteristics, identification, and transportation) will be examined using the Narrative Quality Assessment Tool. Narrative characteristics will be examined using a 9 item scale that measures perceived likability of characters in the story, emotional relevance of the storyline, and cultural elements of the stories. Identification will be examined using a 8-item scale that measures the degree to which participants are able to relate to the characters in the video recordings or perceive their story to be similar to their own. Transportation (engagement) will be examined using a 6-item scale

that measures participants emotional connections to the stories in the video recordings. Response options will be on a 5-pt scale and similar to that in other questionnaires in this pilot (1=not at all to 5=quite a bit). Internal consistency for the three scales range from .92 - .95 respectively. Validity was determined through hypothesized factor structures (CFA). Patients and family caregivers will be asked to complete these evaluations after each intervention session.

Qualitative exploration of usability and transportation will occur after each weekly intervention session. During the qualitative assessments, participants will be asked to express their thoughts, feelings, and opinions of the narrators and describe perceptions of similarity to, identification with narrators in the recordings, and, transportation (engagement) of participants to selected recordings. *Participants and FCG's will also be asked to describe ways in which they might use the strategies from the video recordings to cope with their own cancer experience.* Guided by Transportation Theory, the final selection of recordings will consist of those with higher levels of narrative quality. These stories from actual patients and FCG's and used in this intervention are hypothesized to be relatable and acceptable in content and context. In previous storytelling interventions among African American and Latino populations, *listening* to culturally relevant stories resulted in changes in attitudes and behavior change. We will qualitatively assess usability through perceived navigation (ease of use); content (video length, topics covered, presentation); persuasiveness (mood, encouragement); and, value (time spent, future use, potential recommendations to others). **Description of Intervention:** The intervention will consist of participants viewing a selection of video recorded vignettes during 3 weekly sessions. There will be 5 vignettes included in each session with each vignette edited to a real time of 3-4 minutes (each session is 30 minutes). Since the intervention is designed to be self-administered, there will be a video recorded introduction and instructions for use narrated by the PI. The vignettes are of actual African American cancer survivors narrating stories of ways in which hymns can be used to overcome their *anxieties and depressed moods through the use of a hymn. The hymns included represent exemplars from the 5 themes prevalent in the PI's previous research (see Table 2)*.

**Intervention Group.** In this preliminary study, the intervention will consist of 3 weekly sessions (each session occurs over 30 minutes duration) delivered to the patient and FCG during an outpatient chemo infusion visit. In the **first step**, the RA/PI will review again purpose of the intervention and follow-up data collection. In **step two**, the patient and FCG will be given a link and password to Vimeo video sharing platform to view preselected video recordings representing the 5 categories of hymns. Immediately after each session, the RA/PI will conduct a short open-ended interview with participants to determine participant identification, engagement, and emotional response to the recordings. We will also explore experiences with use of hymns as a coping strategy. This data will assist with the further refinement of the intervention for a future RCT. In **step three**, we will schedule times for subsequent intervention and data collection sessions.

**Informed Consent Process:** The PI will read the consent form by phone or video conference platform unless participants would prefer to read it her/himself. Participants will be permitted to discuss the study with family or friends and ask the PI questions. Once the verbal consent form has been reviewed (or read to participants) the research participant will be asked to express their understanding of the consent form. Participants will be asked to describe their understanding of the study to ensure comprehension of the study. Research subjects will be given a copy of the verbal consent form for their records.

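### Effect sizes meant to guide a future RCT's power calculation will be within-group changes, and four of the five outcomes have no named instrument or outcome-specific time point

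*Combined protocol and SAP*

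**What the plan says.** - **Purpose.** Section 2.c (Sample size justification): "our aim will be to compute effect sizes that will guide power calculation for testing intervention effectiveness in a future RCT".
- **Design.** Section 1 (Study Design) says the study "uses a quasi-experimental (pre-post test, repeated measures) design". Section 2.b recruits 40 dyads in total. The intervention description covers one group, and no comparator appears anywhere.
- **Outcomes.** Section 1 promises effect sizes for psychological distress (primary) and for "spiritual well-being, patient-physician communication, supportive family relationships, and quality of life (secondary outcomes".
- **Measures.** Only HADS, for distress, and the narrative-quality scales, which rate the videos, have both a named instrument and their own timing. HADS is given at baseline and after the sessions.
- **Schedule.** Section 2.e: "Participants will be asked to complete interviews at baseline (time of enrollment into study), after each intervention session, and at 6 weeks". No outcome is assigned to these visits there.
- **Entry level.** Section 2.b admits patients "previously screened and with greater than 0 level of psychological distress". The NCCN Distress Scale paragraph says "We will only recruit patients with a NCCN-DT score of" at least 4.
- **Next step.** The end of section C expects "a future feasibility study that rigorously evaluates a faith-based storytelling intervention". Section 10 (Aim 2) likewise keeps the higher-ranked half of the narratives for later feasibility testing.
- **Analysis.** Section 10 covers descriptive summaries, tests on responses to the videos, and qualitative work. It has no analysis of HADS change.

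**The concern.** An RCT is powered on the difference between arms. A one-group study can only show how far participants moved from their own baseline. In newly diagnosed patients receiving chemotherapy, distress may fall or rise over a few weeks without any intervention. Repeated contact with an interviewer may also shift scores. Patients selected for raised distress will tend to score lower on a second measurement. How strong that last effect might be cannot be judged, because the two entry levels differ.

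If the observed change were carried into the RCT as its target difference, that trial could be too small or too large, and nothing in this study would show which.

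The second issue is delivery. The objective names five outcomes, but for four of them the available text does not let a reader tell what will be measured or when.

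**Working it through.** **The plan's own figure.** Section 2.c gives 80% power for a difference of 0.6 with SD 1, within-subject correlation 0.2, alpha 0.05 and 40 dyads (80 people). It does not state the test, the sidedness or the number of time points. Two-sided t calculations give:
- one group of 40, paired, SD of change = sqrt(2 × (1 − 0.2)) = 1.265: 83.3%;
- all 80 people, paired and treated as independent: 98.7%;
- two groups of 40 at one time point: 75.5%.

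None of these is 80%. The figure is under-specified rather than shown to be wrong, and the point here does not depend on it.

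**What the effect size can be.** 40 dyads × 2 people = 80, so the total sample of 80 counts people, not two arms. With one group, the effect size is the post-session mean minus the baseline mean, divided by an SD. It equals the intervention effect plus whatever change would have happened anyway, and the study cannot separate the two.

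**Illustration for the RCT.** The 0.6 SD is the minimum difference in 2.c, not an observed change. The between-arm differences below are assumptions. Two-sample t-test, two-sided 5%, 80% power, no dropout. Normal approximation: n per arm = 2 × (1.96 + 0.84)² / d². For d = 0.6 this is 15.68 / 0.36 = 43.6, or 44; the t-test needs 45. Power at 45 per arm uses the noncentrality d × sqrt(45/2).

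| Between-arm difference (SD) | Needed per arm | Noncentrality at 45 per arm | Power at 45 per arm |
|---|---|---|---|
| 0.3 | 176 | 1.42 | 29% |
| 0.4 | 100 | 1.90 | 47% |
| 0.6 | 45 | 2.85 | 80% |
| 0.8 | 26 | 3.79 | 96% |

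The last row covers the case where distress would have risen without the intervention. The RCT would then be larger than needed.

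**Precision of the change with 40 dyads** (SD 1, correlation 0.2, one post measurement, t(0.975, 39) = 2.023):
- one role: 2.023 × sqrt(1.6/40) = 0.40 SD;
- both roles pooled: 2.023 × sqrt((1.6/80) × (1 + r)), where r is the within-dyad correlation of change. This is 0.29 at r = 0, 0.35 at r = 0.5 and 0.40 at r = 1 (range of r assumed).

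If HADS were given after each of the three sessions and at 6 weeks, and the four post scores averaged, the variance of the change would be 1 + (1 + 3 × 0.2)/4 − 2 × 0.2 = 1.0. The one-role half-width would be 2.023 × sqrt(1.0/40) = 0.32 SD.

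**The four secondary outcomes.** No instrument is named for spiritual well-being, patient-physician communication, supportive family relationships or quality of life. The religiosity scale does not fill the gap: it counts spiritual practices and is collected before the videos are viewed. The narrative-quality paragraph mentions other questionnaires in the pilot with a similar 5-point response format, but does not name them. They cannot be HADS: 14 items forming two subscales of 0-21 give at most 42/14 = 3 points per item.

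**HADS timing.** The HADS paragraph can be read as one assessment when the sessions are finished or one after every session. Neither that paragraph nor section 2.e says whether HADS is repeated at 6 weeks.

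**The case against.** The strongest reply is that the main harm depends on a use the plan never states. Effect sizes are to guide a power calculation; nothing says the pre-post change becomes the target difference. The design is openly labelled quasi-experimental, and further feasibility testing is expected first. The RCT sentence in the intervention description follows the open-ended interviews and concerns refining content, so only 2.c links effect sizes to an RCT. All of this stands. A reader might infer that the future RCT will be underpowered; the documents do not support that. The direction of any error is unknown and the background change is assumed.

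It is also fair that wide intervals are ordinary small-sample imprecision. They would arise with a comparator too and are not evidence of confounding.

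On the secondary outcomes, a reader might infer that they are not measured at all. That goes too far. Section 2.e gives a general schedule whose interviews include quantitative measures, and unnamed questionnaires are mentioned. The supportable statement is that no instrument or outcome-specific time point is named.

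The plan also offers an external yardstick: "These points will also allow for comparisons with other long-term investigations of psychological distress among cancer patients". This is a weak comparison, and no method is given for it.

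What the reply does not remove is that 2.c makes effect sizes for RCT planning the purpose of the sample size, and one group cannot supply a between-arm effect.

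**Conclusion.** The point holds in a limited form. The effect size available from this study is a within-group change, and it does not estimate the difference an RCT is powered on. The consequence is conditional on how the change is used: 29-47% power for an RCT of 45 per arm sized on 0.6 SD, if the between-arm difference is 0.3-0.4 SD. Even leaving bias aside, the change would be known only to within 0.29-0.40 SD with a single post measurement, under the SD and correlation in 2.c.

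Two further statements hold without any assumption. Four of the five outcomes listed for effect sizes have no named instrument or outcome-specific time point in the available text. The patient distress entry level is above 0 in one place and at least 4 in another.

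Aims 1 and 2 (developing the videos, and their usability and acceptability) are not affected. The changes should be made, but they do not call the study itself into question.

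**What to change.** 1. **Section 2.c.** State that the within-group HADS change will be reported descriptively with its 95% CI and will not be taken as the target difference of a future RCT. State that the HADS SD, the within-person and within-dyad correlations, and retention will inform planning, and give their imprecision. Per role with n = 40, the 95% limits for the SD run from about 18% below to 28% above the estimate, and an observed correlation of 0.2 has a 95% CI of −0.12 to 0.48.
2. **Section 1.** Limit the effect-size objective to outcomes that are measured. If the four secondary outcomes are in the unnamed questionnaires, identify each scale and its time points. If they are not, remove them from the objective.
3. **Consistency.** Reconcile section 2.b with the NCCN Distress Scale paragraph on the entry level; this review does not choose between them. Reconcile section 2.e with the HADS paragraph on when HADS is given, and name the time point used for the change.
4. **Minor.** Add the HADS change analysis to section 10, by role or pooled with allowance for dyad clustering.

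**Cost.** This needs only wording and one analysis line, with no extra participants or visits. The downside is that the study no longer claims to supply the RCT effect size directly, and the planning inputs it does supply are imprecise. If the four outcomes are not already being collected and the sponsor wants to keep them, the scales would add to interviews already put at about 45 minutes.
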